5.5. Justification for Dose

The bolus dose of insulin lispro (LY900014 or Humalog) will be individualized per patient to cover the carbohydrate content in this standardized liquid test meal. This dose of insulin is reflective of a clinically relevant, individualized insulin dosing, similar to how patients would determine the insulin dose for the carbohydrate content in a meal. For each patient, the individualized prandial insulin lispro dose in LY900014 and Humalog for each test meal must be kept identical throughout the crossover periods.

6. Study Population

Eligibility of patients for study enrollment will be based on the results of screening medical history, physical examination, vital signs, clinical laboratory tests, and electrocardiogram (ECG).

The nature of any conditions present at the time of the physical examination and any preexisting conditions will be documented.

Screening may occur over a 14 day period prior to the lead-in site visit. Patients who are not entered within this time period, may be subjected to an additional medical assessment and/or clinical measurements to confirm their eligibility.

Prospective approval of protocol deviations to recruitment and enrollment criteria, also known as protocol waivers or exemptions, are not permitted.

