10.1. Sample Size Determination

An initial 36 patients may be enrolled in order that approximately 30 patients complete the study. Thirty completing patients will provide greater than 95% power to demonstrate a 2-fold increase in the serum insulin lispro AUC(0-30min) between LY900014 and the Humalog. Testing will be done at an alpha level of 0.05 with a 2-sided confidence interval (CI). The sample size will also provide greater than 95% power to demonstrate a 35% reduction of early 50% t_{max} . The estimated standard deviation of within-subject difference on the log scale is 0.35 for AUC(0-30min) and 0.25 for early 50% t_{max} , according to an analysis of internal Lilly data (Study I8B-FW-ITRG [ITRG]) for LY900014 and Humalog administered in a repeat-dose study.

With this sample size, there is approximately 80% power to detect a -30 mg·h/dL difference (LY900014 versus Humalog when both are given immediately before meals) in postprandial glucose Δ AUC[0-2h]. This is based on an analysis of ITRG which showed a standard deviation of within-patient difference of 56.20 mg·h/dL on the original data scale.

Patients who are randomized but drop out before completing assigned treatment may be replaced to ensure that approximately 30 patients complete the study.

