10.3. Statistical Analyses

Statistical analysis of this study will be the responsibility of Eli Lilly and Company or its designee.

Primary statistical analyses of PK and GD parameters will be conducted on the set of patients who complete all treatment periods as the PK parameters and GD response is dependent on the insulin dose which is individualized by patient. Supportive analyses may be done on the key parameters for the patients who complete at least one period of treatment.

Any change to the data analysis methods described in the protocol will require an amendment only if it changes a principal feature of the protocol. Any other change to the data analysis methods described in the protocol and the justification for making the change will be described in the study results.

Safety analyses will be conducted on the set of patients receiving at least 1 dose of the study drug to which they are randomized, regardless of whether or not they completed all protocol requirements.

Unless otherwise noted, all tests of treatment effects will be conducted at a 2-sided alpha level of 0.05, and CIs will be calculated at 95%, 2-sided.

Additional exploratory analyses of the data will be conducted as deemed appropriate. Study results may be pooled with the results of other studies for population PK analysis purposes to avoid issues with post-hoc analyses and incomplete disclosures of analyses.

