10.3.2. Pharmacokinetic Analyses

10.3.2.1. Pharmacokinetic Parameter Estimation

Patients who complete at least 1 MMTT and have measurable insulin lispro concentrations will be included in the analysis dataset for the PK analyses. PK analyses will be conducted using standard noncompartmental methods of analysis (CCI ██████████) on a computer that meets or exceeds the minimum system requirements for these programs. It is possible that other validated equivalent PK software programs may be utilized if appropriate, warranted, and approved by global PK management. The version of any software used for the analysis will be documented, and the program will meet the Lilly requirements of software validation.

Free serum insulin lispro concentrations will be used to calculate several PK parameters, including early 50% t_{max} , time to late half-maximal drug concentration (late 50% t_{max}), maximum observed drug concentration (C_{max}), time to maximum observed drug concentration (t_{max}), $t_{1/2}$, AUC from time zero to time t , where t is the last time point with a measurable concentration [AUC(0-tlast)], AUC from time 0 to 30 minutes [AUC(0-30min)], AUC from time

zero to 1 hour [AUC(0-1h)], AUC from time zero to 7 hours [AUC(0-7h)], AUC from time 3 to 7 hours [AUC(3-7h)] and AUC from time zero to infinity [AUC(0-∞)]. In addition, the apparent total body clearance of drug calculated after extra-vascular administration (CL/F), and volume of distribution after extra-vascular administration (Vz/F) also will be determined. Other parameters may be calculated as deemed appropriate. Additional partial AUCs may be computed as necessary, such as AUC from time zero to 2 hours.

The insulin lispro PK parameters for assessing faster insulin lispro absorption are the early 50% t_{max} and AUC(0-30min).

Although attempts will be made to adhere to the scheduled collection times, it is recognized that situations arise that may compromise sample collection at the scheduled times. Parameters will be individually calculated for each patient based on actual collection times and presented by summary statistics.

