9. STATISTICAL METHODOLOGY

9.1 General

Data listings will be provided for all data that is databased. Summary statistics and statistical analysis will only be presented for data where detailed in this SAP. For continuous data, summary statistics will include the arithmetic mean, arithmetic SD, median, min, max and N; for log-normal data (e.g. the PK parameters: AUCs and maximum observed drug concentration [C_{max}]) the geometric mean and geometric coefficient of variation (CV%) will also be presented. For categorical data, frequency count and percentages will be presented. Data listings will be provided for all subjects up to the point of withdrawal, with any subjects excluded from the relevant population highlighted. Summary statistics and statistical analyses will generally only be performed for subjects included in the relevant analysis population. For the calculation of summary statistics and statistical analysis, unrounded data will be used.

Mean change from baseline is the mean of all individual subjects' change from baseline values. Each individual change from baseline will be calculated by subtracting the individual subject's baseline value from the value at the sequential timepoints. The individual subject's change from baseline values will be used to calculate the mean change from baseline.

Data analysis will be performed using 

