9.3.2 Pharmacokinetic Statistical Inference

Patients who did not keep identical insulin lispro doses for both treatments (LY900014 and Humalog) will be excluded from the statistical analysis of the PK parameters.

Log-transformed AUCs and C_{max} for insulin lispro will be evaluated to estimate geometric means, ratios of geometric means of insulin lispro within LY900014 to Humalog, and their corresponding 95% CIs of the ratios using the mixed-effects model that includes treatment (LY900014, Humalog) and period as fixed effects and patient as a random effect.

Example SAS code:

```
proc mixed data=pk;  
class patient period treatment;
```

```
model logpk = treatment period / ddfm=kr alpha=0.05;  
random patient;  
lsmeans treatment;  
run;
```

For AUC(0-∞), the analysis above will be used to produce an assessment of within-patient and between-patient variability for each treatment.

The same model without log transformation will be used for the analysis of the PK time parameters (early 50% t_{max} , late 50% t_{max} , and t_{max}). Least-squares means (LSmeans), treatment differences in LSmeans, and the corresponding 95% CIs for the treatment differences will be estimated from the model. The p-value on the difference between LSmeans will be used to determine statistical significance. The treatment ratios and 95% CIs for the ratios will be calculated using Fieller's theorem (Chow and Liu 2009).

Statistical significance will be achieved when the p-value for a test is less than 0.05.

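### SAP 9.3.2 takes the between-patient variability of AUC(0-∞) from raw AUC, so it mixes the spread of individualized doses with the variability of exposure per unit dose

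*SAP*

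**What the plan says.** Protocol 5.5 states that the lispro dose "will be individualized per patient to cover the carbohydrate content in this standardized liquid test meal". Protocol 5.5 and 7.2.1 require the dose to be the same at every test meal for a given patient. Protocol 10.3 acknowledges that the "PK parameters and GD response is dependent on the insulin dose which is individualized by patient".

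SAP 9.3.2 models log AUC and log Cmax with treatment and period as fixed effects and patient as a random effect. For AUC(0-∞), that analysis "will be used to produce an assessment of within-patient and between-patient variability for each treatment". The example code has one random patient intercept and one residual variance. Dose appears neither as a covariate nor as a divisor. Patients whose doses differed between the products are excluded. SAP 9.2 lists and summarises the selected MMTT dose but does not link it to exposure.

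Protocol 10.3.2.1 and 10.3.2.2 plan CL/F as a PK parameter, analysed on the log scale in the same model. SAP 9.3.1 and 9.3.2 do not mention it, and SAP 11 reports no departure from the protocol's analyses.

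**The concern.** CL/F is dose divided by AUC(0-∞), so log AUC(0-∞) = log dose − log CL/F. Log dose is constant within a patient and differs between patients. Its whole variance, and its covariance with log CL/F, therefore enters the patient variance component and no other. The exclusion of unequal doses protects the within-patient contrast but does nothing for this component.

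A reader of the study report would probably take a between-patient CV given for each product as a property of the product. It would in fact be a mixture of how differently patients were dosed and how variable their exposure is per unit dose. A dose component common to both products can also make their between-patient variabilities look more alike in relative terms than they are per unit dose.

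**Working it through.** **The plan's own figures.** The documents state no variability for AUC(0-∞), so there is no figure of that kind to reproduce. The sample-size statements in Protocol 10.1 do reproduce. With 30 completers, a difference of 30 and an SD of 56.20 mg·h/dL, a two-sided paired t-test at 0.05 has power 0.807 (stated: about 80%). Power is above 0.999 for both AUC(0-30min) and early 50% tmax (stated: above 95%). These rest on within-patient differences, in which dose cancels.

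**Formula.** From the identity above,

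Var(log AUC) = Var(log dose) + Var(log CL/F) − 2ρ·SD(log dose)·SD(log CL/F),

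where ρ is the correlation of log dose with log CL/F. For log-normal quantities Var = ln(1 + CV²) and CV = √(exp(Var) − 1).

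**Assumed inputs, none of them in the documents.** CL/F CV 25% (log-variance 0.0606); dose CV 20% to 50%; ρ of 0 or 0.5.

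| Dose CV | Var(log dose) | Reported CV, ρ = 0 | Dose share of variance, ρ = 0 | Reported CV, ρ = 0.5 |
|---|---|---|---|---|
| 20% | 0.0392 | 32.4% | 39% | 22.9% |
| 30% | 0.0862 | 39.8% | 59% | 27.8% |
| 40% | 0.1484 | 48.2% | 71% | 34.8% |
| 50% | 0.2231 | 57.3% | 79% | 42.7% |

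First row, ρ = 0: 0.0392 + 0.0606 = 0.0998, CV 32.4%. With ρ = 0.5, subtract √(0.0392 × 0.0606) = 0.0488. The unrounded remainder is 0.0511, CV 22.9%, which is below the assumed 25%. Over a wider grid at ρ = 0 (dose CV 20% to 60%, CL/F CV 20% to 40%), the dose share runs from 21% to 89%.

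**Relative difference between products.** Assume CL/F CVs of 20% and 30% for the two products: log-variances 0.0392 and 0.0862, ratio 2.20, difference 0.047. Add a dose CV of 40%:

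- ρ = 0: 0.1876 and 0.2346, that is CVs of 45.4% and 51.4%. The ratio falls to 1.25; the difference stays at 0.047.
- ρ = 0.5: 0.1876 − 0.0763 = 0.1113 and 0.2346 − 0.1131 = 0.1215, that is CVs of 34.3% and 35.9%. The ratio is 1.09 and the difference 0.0102.

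The absolute difference is therefore preserved only when dose is independent of CL/F.

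**Pooled variances.** In simulated trials of 30 patients with two administrations of each product, CL/F CVs of 20% and 30% and a dose CV of 40%, the example model returned a single between-patient CV: 47% on raw AUC and 24% on AUC/dose. Neither is a figure for each product. Dividing by dose does not cure this.

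**What does not change.** With complete data every patient contributes both products in all four periods, so treatment and period contrasts are entirely within-patient. Subtracting a patient constant from log AUC leaves the ratios, confidence intervals, p-values and residual variance as they were.

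**The case against.** **Raw AUC may be the intended quantity.** SAP 9.3.1 makes AUC(0-∞) the key parameter for total exposure, and Protocol 5.5 presents the dose as clinically relevant individualized dosing. The spread of raw AUC is then the spread of exposure actually achieved, a legitimate quantity. This stands, and is why the raw figure should be kept and labelled rather than replaced.

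**The figure need not be mostly dose spread.** A reader might infer that it is. The documents do not support that: they give no dose distribution, the dose share depends on the assumptions, and a positive dose-clearance correlation pulls the reported CV down. Such a correlation is plausible when dose follows need and BMI may range from 18.5 to 35.0 kg/m² (Protocol 6.1), but it is not documented.

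**A product difference is not shown to be hidden.** A reader might infer that too. The plan contains no comparison of between-patient variances, and the example code produces no separate figures to compare. Only shrinkage of the relative difference can be claimed, and only once treatment-specific variances are fitted.

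**The protocol planned CL/F for geometric means and ratios, not for variability.** Correct. Its undeclared absence is a discrepancy in its own right and does not make this assessment a departure from the protocol. It does remove the one planned dose-scaled measure of total exposure.

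**The material for adjustment is available.** Doses are listed, and SAP 9.3.1 permits further parameters, so AUC/dose could be derived without an amendment. Permission is not a plan, however, and a marginal dose summary does not supply the covariance.

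**SAP 9.1 need not change.** For AUCs and Cmax it says that the "geometric mean and geometric coefficient of variation (CV%) will also be presented". The same arithmetic applies to a CV across patients, but this is a routine summary not presented as a product property.

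**Conclusion.** The concern holds as a matter of algebra: the planned between-patient variability of AUC(0-∞) combines dose variance, CL/F variance and their covariance, and the raw output cannot separate them. Its size is not determinable from the documents. Under the stated assumptions a true CV of 25% would be reported as anything from 23% to 57%, so inflation is possible but not certain.

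The reach is limited. The assessment serves no listed endpoint, and the primary endpoints and sample size are untouched. Separately, the example code cannot deliver variability for each treatment, whatever response is used. This is a worthwhile correction to a pre-specified descriptive output, not a threat to the trial's conclusions.

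**What to change.** - In SAP 9.3.2, report the AUC(0-∞) variability assessment on log(AUC(0-∞)/dose), equivalently −log(CL/F). Keep the raw-AUC figure beside it, labelled as exposure achieved under individualized dosing.
- For this assessment, fit treatment-specific patient and residual variances, for example with RANDOM and REPEATED statements grouped by treatment, or an unstructured treatment covariance for patient with treatment-specific residuals. Each product is given twice per patient, and SAP 8 takes PK to be unaffected by meal timing, so the two administrations serve as replicates.
- Keep raw AUC and the existing model for the treatment ratios.
- Restore CL/F to SAP 9.3.1 and 9.3.2, or declare and justify its removal in SAP 11.

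The cost is one derived variable, one additional model output and a few lines of text. The dose is already recorded, and AUC(0-∞) is already being computed.

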9.4 Glucodynamic Analyses

9.4.1 Glucodynamic Parameter Estimation

Patients who receive at least 1 dose of study drug and have evaluable GD data will be included in the analysis set for the GD analyses.

Data will be analyzed for the patients during each MMTT. The change from baseline values (the average of -30, -15, and 0 minutes represented as the 0-hour time point prior to the start of the MMTT) for each patient will be calculated. The area under the baseline subtracted glucose concentration versus time curve from time 0 to 2 hours ($\Delta AUC[0-2h]$) and area under the baseline subtracted glucose concentration versus time curve from time 0 to 5 hours post meal ($\Delta AUC[0-5h]$) will be calculated. In addition, the change from baseline maximum glucose observed during the 5 hours postmeal and change from baseline 1 hour glucose and 2 hour glucose post the start of the meal will be calculated. Other partial $\Delta AUCs$ may be calculated, as deemed appropriate. Parameters will be individually calculated for each patient and presented by summary statistics. Glucose values post an intervention for either a hypoglycemic or hyperglycemic event during the MMTT will be excluded from the GD analysis.

9.4.2 Glucodynamic Statistical Inference

Patients who did not complete the entire meal or had significant changes in nutrient consumption of the standardized liquid test meal or dose changes during the MMTTs across periods included in the statistical analysis will be excluded from all the statistical analyses of the GD parameters. Patients which don't have evaluable data for both treatments (Humalog and LY900014) for each injection-to-meal timing (immediately before the start of meal or 20 minutes after the start of the meal) will be excluded from the statistical analysis of the PD parameters.

Summary statistics (including number of patients, mean, SD or standard error, minimum, and maximum) will be presented by treatment and by timing of dose (all 4 combinations of treatment and timing of dose).

The GD parameters on the original scale (not log-transformed) will be analyzed using a statistical model that includes treatment, timing of dose (0 [immediately before the test meal], 20 minutes following the start of test meal), treatment-by-timing of dose interaction, and period as fixed effects and patient as a random effect. The p-value on the difference between LSmeans will be used to determine statistical significance and the corresponding 95% CIs for the LSmean ratios from Fieller's theorem will be presented.

Example SAS code:

```
proc mixed data=gd;
class patient period treatment timing;
model gd = treatment timing period treatment*timing / ddfm=kr
alpha=0.05;
random patient;
lsmeans treatment*timing;
run;
```

Statistical significance will be achieved when the p-value for a test is less than 0.05.

9.5 Safety and Tolerability Assessments

9.5.1 Adverse events

Where changes in severity are recorded in the Case Report Form (CRF), each separate severity of the adverse event (AE) will be reported in the listings, only the most severe will be used in the summary tables. A pre-existing condition is defined as an AE that starts before the subject has provided written informed consent and is ongoing at consent. A non-treatment emergent AE is defined as an AE which starts after informed consent but prior to dosing. A treatment-emergent AE is defined as an AE which occurs postdose or which is present prior to dosing and becomes more severe postdose.

All AEs will be listed. Treatment-emergent AEs will be summarized by treatment, severity and relationship to the study drug. The frequency (the number of AEs, the number of subjects experiencing an AE and the percentage of subjects experiencing an AE) of treatment-emergent AEs will be summarized by treatment, Medical Dictionary for Regulatory Activities (MedDRA) version 20.0 system organ class and preferred term. The summary and frequency AE tables will be presented for all causalities and those considered related to the study drug. Any serious AEs will be tabulated.

9.5.2 Concomitant medication

Concomitant medication will be coded using the WHO drug dictionary (Version March 2017). Concomitant medication will be listed.

9.5.3 Clinical laboratory parameters

All clinical chemistry, hematology and urinalysis data will be listed. Additionally clinical chemistry, hematology and urinalysis data outside the reference ranges will be listed.

Values for any clinical chemistry, hematology and urinalysis values outside the reference ranges will be flagged on the individual subject data listings.

9.5.4 Vital signs

Vital signs data will be summarized by treatment together with changes from baseline, where baseline is defined as Day 1 predose for each period. Furthermore, values for individual subjects will be listed.

9.5.5 Electrocardiogram (ECG)

The ECG data will be listed for individual subjects.

9.5.6 Hepatic Monitoring

If a subject experiences elevated alanine aminotransferase (ALT) $\geq 3 \times$ upper limit of normal (ULN), alkaline phosphatase (ALP) $\geq 2 \times$ ULN, or elevated total bilirubin (TBL) $\geq 2 \times$ ULN, liver tests will be performed to confirm the abnormality.

The subjects' liver disease history and associated person liver disease history data will be listed. Any concomitant medication of acetaminophen/paracetamol will be listed. Results from any hepatic monitoring procedures, such as a magnetic resonance elastography (MRE) scan, and a biopsy assessment will be listed, if performed.

Hepatic risk factor assessment data will be listed. Liver related signs and symptoms data will be summarized by treatment and listed. Alcohol and recreational drug use data will also be listed.

All hepatic chemistry, hematology, coagulation, and serology data will be listed. Values outside the reference ranges will be flagged on the individual subject data listings.

9.5.7 Blood Glucose Monitoring and Hypoglycemia

Hypoglycemic events will be appropriately recorded in the CRF. In the case of a hypoglycemic event, the actual blood glucose value, if measured, will be recorded in the CRF, together with any treatments administered. All hypoglycaemic events will be listed and summarized by treatment (LY900014 or Humalog) and dosing time. Each hypoglycaemic event will be ascribed in causality to the most recent meal-time insulin administration, including Humalog during lead-in, investigational product during MMTTs, Humalog between periods, or patient's own insulins taken during follow up.

The categories of Hypoglycemia are defined as follows:

- **Documented Glucose Alert Level (Level 1)**, Plasma Glucose (PG) ≤ 70 mg/dL (3.9 mmol/L):
 - **Symptomatic hypoglycemia**: an event during which typical symptoms of hypoglycemia are accompanied by PG ≤ 70 mg/dL (3.9 mmol/L)

- **Asymptomatic hypoglycemia:** an event not accompanied by typical symptoms of hypoglycemia but with PG ≤ 70 mg/dL (3.9 mmol/L)
- **Unspecified hypoglycemia:** an event during which PG ≤ 70 mg/dL (3.9 mmol/L) but no information relative to symptoms of hypoglycemia was recorded
- **Documented Clinically Significant Hypoglycemia (Level 2)** PG < 54 mg/dL (3.0 mmol/L):
 - **Symptomatic hypoglycemia:** an event during which typical symptoms of hypoglycemia are accompanied by PG < 54 mg/dL (3.0 mmol/L)
 - **Asymptomatic hypoglycemia:** an event not accompanied by typical symptoms of hypoglycemia but with PG < 54 mg/dL (3.0 mmol/L)
 - **Unspecified hypoglycemia:** an event during which PG < 54 mg/dL (3.0 mmol/L) but no information relative to symptoms of hypoglycemia was recorded
- **Severe hypoglycemia (Level 3):** an event requiring assistance of another person to actively administer carbohydrate, glucagon, or other resuscitative actions. During these episodes, the patient has an altered mental status and cannot assist in their care, is semiconscious or unconscious, or experienced coma with or without seizures and may require parenteral therapy. PG measurements may not be available during such an event, but neurological recovery attributable to the restoration of blood glucose concentration to normal is considered sufficient evidence that the event was induced by a low PG concentration (PG ≤ 70 mg/dL [3.9 mmol/L])
 - **Severe hypoglycemia requiring medical attention:** a severe hypoglycemic event when patients require therapy by HCPs (EMTs, emergency room personnel, etc)

Other Hypoglycemia:

- **Nocturnal hypoglycemia:** any hypoglycemic event (documented symptomatic, asymptomatic, probable symptomatic, or severe hypoglycaemia) that occurs between bedtime and waking
- **Relative hypoglycemia:** an event during which typical symptoms of hypoglycemia, which do not require the assistance of another person, are accompanied by PG > 70 mg/dL (3.9 mmol/L), but these levels may be quickly approaching the 70 mg/dL (3.9 mmol/L) threshold
- **Overall (or total) hypoglycemia:** This optional category combines all cases of hypoglycemia. If an event of hypoglycemia falls into multiple subcategories, the event is counted only once in this category

- **Probable symptomatic hypoglycemia:** An event during which symptoms of hypoglycemia are not accompanied by a PG measurement but that was presumably caused by a blood glucose concentration ≤ 70 mg/dL (3.9 mmol/L).

